7.2 PAYMENT

Participants will be paid \$20 each for completing the one-time baseline (including ineligible participants), pre, and follow-up assessments and \$30 for completing the post assessment. For the twice weekly assessments, participants will be reimbursed on a payment schedule similar to one used in a previous study including \$5 for each completed assessment with bonuses for high compliance rates.³⁴ Participants will not be reimbursed for intervention sessions.

8 STATISTICAL ANALYSES

To analyze the primary outcome, GAS, we will use a variation of multi-level modeling (MLM) tailored to analyze single- case experimental design data.⁵⁸ The appropriateness of the model will be evaluated and adapted as needed to fit the data including evaluating and implementing covariance structures to accommodate autocorrelation such as an auto- regressive error structure. We will evaluate alternative models to assess model assumptions and robustness of treatment effects. These analyses will be supplemented with visual inspection by graphing participants' outcomes in a multiple- baseline design format throughout the study.⁵⁹ Graphs will be aligned across participants in order to establish temporal precedence of symptom change and intervention onset and demonstrate replication across participants within the sample. MLM and visual analysis of the primary outcomes will be supplemented with a non-overlap of all pairs effect size.⁶⁰ Other quantitative outcomes will be analyzed through descriptive statistics, and will be used to generate pre-post effect size estimates for Veteran outcomes to establish initial estimates of efficacy for power estimates.

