1 PROTOCOL SUMMARY

1.1 SYNOPSIS

Title:	Peer-Delivered Whole Health Coaching to Improve Recovery in Veterans with PTSD
Study Description:	This project implemented peer-delivered Whole Health Coaching with
	Veterans experiencing clinically significant PTSD symptoms but who chose
	not to engage in specialty mental health. This project utilizes a
	concurrent/non-concurrent multiple baseline design across subjects to
	investigate patient outcomes (specifically, goal attainment) before, during,
	and after Whole Health Coaching.
Objective:	Identify changes in Veterans' health and wellness behaviors after Whole
	Health Coaching.
Primary Outcome:	Goal Attainment Scaling
Secondary Outcomes:	PTSD Checklist for DSM-5 (PCL-5)
	Inventory of Psychosocial Functioning (IPF)
	Client Satisfaction Questionnaire-8 (CSQ-8)
Study Population:	Veterans enrolled in primary care at participating sites with probable PTSD
	defined as screening positive for a Criterion A event and PCL-5 score 33 or
	higher.
Description of	Syracuse VA Medical Center and Affiliated Community Based Outpatient
Sites/Facilities Enrolling	Clinics
Participants:	
Description of Study	Whole Health Coaching is a Veterans Health Administration variation of
Intervention:	integrative health coaching. For this study it will be administered by a peer
	support specialist.
Study Duration:	1 May 2018-31 October 2019
Participant Duration:	24 weeks

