3 STUDY DESIGN

This is a quantitative project with a minor qualitative component. This project will use a multiplebaseline design across participants with non-concurrent replications to measure the impact of Whole Health Coaching on Veterans' progress toward health and wellness goals. In this design, outcomes are monitored over time prior to the onset of an intervention, to establish a baseline, and after the onset of an intervention to evaluate changes in outcomes for each participant.³² In addition, the start of the intervention is staggered across participants to demonstrate experimental control (i.e., that the intervention and not some other extraneous variable was responsible for any changes that were observed). Data from each participant's intervention phase are compared to that person's baseline phase (within-series comparisons) and to the overlapping portions of other participants' baseline phases who have not yet begun the intervention (between-series comparisons). We plan to recruit so that Veterans start baseline in groups of 2-3 and move through the study concurrently. Participants who start baseline concurrently will be randomized to different baseline lengths to establish temporal precedence of change and control for history effects.³² The minimum baseline length of 4 weeks (eight possible assessment points) allows for sufficient assessments for the statistical model. Intervention will be introduced when each participant meets a baseline stability criterion defined as at least four data points total, the final two of which fall within the range of the previous data points (i.e., no increasing slope or trend over the final three baseline data points). There will be flexibility to extend baseline by one week if

participants have not met the stability criterion. The maximum possible baseline will be 13 weeks. Following the baseline period, participants will complete ongoing twice weekly assessments throughout the 8 week peer-delivered Whole Health Coaching phase, and 3-12 week post-intervention phase for the remainder of the 24-week study period.

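### Section 8 reports raw NAP and writes out no time term for the GAS model, so slow drift could be credited to coaching; the role of post-intervention ratings is also unstated

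*Combined protocol and SAP*

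**What the plan says.** The Synopsis (1.1) sets the aim: to "investigate patient outcomes (specifically, goal attainment) before, during" and after coaching.

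Section 3 sets the comparison. Each person's coaching ratings are set against that person's own baseline, and against the overlapping baselines of people not yet coached. Participants who start together "will be randomized to different baseline lengths to establish temporal precedence of change and control for history effects". Coaching starts once a stability rule is met: at least four ratings, the last two inside the range of the earlier ones. The rule is glossed as "no increasing slope or trend over the final three baseline data points". Twice-weekly ratings continue through 8 weeks of coaching and a "3-12 week post-intervention phase for the remainder of the 24-week study period".

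Section 8 names an MLM for single-case data and says "The appropriateness of the model will be evaluated and adapted as needed to fit the data". The one model feature it names is the error covariance, for example an autoregressive structure. It promises alternative models without naming any. The staggered starts appear only in the visual analysis: "Graphs will be aligned across participants in order to establish temporal precedence of symptom change and intervention onset". The effect size is added in one sentence: "MLM and visual analysis of the primary outcomes will be supplemented with a non-overlap of all pairs effect size". No trend adjustment is given for NAP and no time term for the MLM. Neither section says whether post-intervention ratings enter the MLM or NAP.

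**The concern.** NAP is the share of baseline-coaching rating pairs in which the coaching rating is better, with ties counted as half. Coaching ratings always come later, so any steady improvement over time raises NAP even if coaching does nothing. An MLM with a phase step and no time term has the same weakness. An autoregressive error structure models serial correlation, not a trend in the mean.

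All of the 8-10 planned completers are coached, so drift is a rival explanation for any improvement. Section 2.2 itself allows that assessment contacts may lead to change. The design's answer is the randomised stagger, which is what allows trend and effect to be separated, but Section 8 does not tie it to either numerical analysis. At stake is whether the reported effect size, and the estimate taken from the primary model, can be read as due to coaching.

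**Working it through.** **1. The plan's own figures.** 4 weeks x 2 ratings = 8 baseline ratings. Post phase: 24 - 8 - 13 = 3 weeks to 24 - 8 - 4 = 12 weeks. Both reproduce. The full series has 24 x 2 = 48 ratings (47 intervals), of which 16 fall in coaching.

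**2. Inputs.** From Sections 3 and 4: twice-weekly ratings, baselines of 4-12 weeks plus a possible one-week extension, the stability rule, concurrent groups of 2-3, and 8-10 completers (9 used, in three trios). Assumed, because the documents give none: linear drift D in within-person SDs over 24 weeks, autocorrelation 0.4 (range 0.2-0.6), a two-sided 5% test, continuous ratings, and no coaching effect except in step 6.

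**3. Raw NAP.** For independent normal ratings, expected NAP is the mean over all pairs of Φ(D x gap / (47√2)), with the gap in rating intervals. With a b-week baseline the mean gap is b + 8. If post ratings are pooled with coaching it is 24 for every b. Check at b = 8, D = 1: 16/47 = 0.340, and Φ(0.340/1.414) = Φ(0.241) = 0.595. Full sums:

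| Drift (SD) | 4 wk | 8 wk | 13 wk | Post ratings pooled |
|---|---|---|---|---|
| 0.5 | 0.536 | 0.548 | 0.563 | 0.571 |
| 1 | 0.571 | 0.595 | 0.623 | 0.639-0.640 |
| 2 | 0.639 | 0.682 | 0.729 | 0.752-0.756 |

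Simulated trials with autocorrelation 0.4 and the stability rule average 0.55, 0.59 and 0.68 (pooled: 0.57, 0.64 and 0.75). The no-effect value is 0.50.

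**4. Stability rule.** If only the range condition is applied, 71% of baselines pass at schedule without drift and 69% with 2-SD drift; after the extension, 91% and 90%. On a stricter reading (also, last rating not above the third-last), the figures are 35% and 36%, then 62% and 64%. The rule barely distinguishes the two cases.

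**5. MLM without time.** Drift enters the step as about D(b + 8)/47. At b = 8 this is 0.17, 0.34 and 0.68 SD for D = 0.5, 1 and 2. Rejection at autocorrelation 0.4:

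| Analysis | 0.5 SD | 1 SD | 2 SD |
|---|---|---|---|
| REML mixed model, baseline and coaching | 7% | 30% | 85% |
| Two-stage (per-person effects, then a t test on 8 df), baseline and coaching | 13-15% | 37-39% | 89-90% |
| Post ratings as a separate step, either method | 8-14% | 35-39% | 90-93% |
| Post ratings pooled with coaching | 20-32% | 77-79% | 100% |

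The REML test is conservative (about 2% at zero drift). Across autocorrelation 0.2-0.6 it rejects 5-12%, 15-47% and 55-96%. With a common time term it rejects 1-3%.

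**6. What adjustment does.** Under drift alone, trend-adjusted NAP stays at 0.49-0.51. For a 1-SD step plus 1-SD drift, raw NAP is 0.82 and adjusted NAP is 0.76; without drift, raw NAP for that step is also 0.76. For a linear rise to 1 SD during coaching, NAP is 0.64 raw, 0.53 if one common slope is removed, and 0.64 if the slope comes from a model with phase-by-time.

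MLM power (REML), baseline and coaching ratings only:

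| True effect | No time | Time + step | Phase-by-time: phase average | Phase-by-time: end of phase |
|---|---|---|---|---|
| 0.5-SD step | 67% | 29% | not run | not run |
| 1-SD step | 100% | 91% | 70% | 33% |
| Rise to 1 SD | 67% | 2-3% | 21% | 33% |
| Rise to 2 SD | 99% | 3% | 76% | 91% |

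**The case against.** Much of the case on the other side stands.

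- A reader might infer that the plan sets no phases or comparison at all. It does: Section 3 names coaching against own baseline, plus the between-series comparison. No text proposes pooling post ratings with coaching, so the pooled figures show only what the silence leaves open.
- A reader might infer that Section 8 prescribes an MLM without time. It does not. It allows adaptation and alternative models, and the methods source it cites, which is not part of the documents, may set the fixed effects. Most of the missing model detail is missing detail and no more.
- The design has real protection in its randomised baselines, and aligned graphs could reveal drift.
- NAP is a supplement, and no text makes 0.50 a benchmark.
- Requiring time plus a step would be a poor remedy. Section 2.1 describes coaching that moves at the Veteran's pace, so gradual response is plausible, and that model has almost no power for it.
- GAS is an anchored scale. Rounding to five levels (an assumption) lifts stability pass rates at schedule from 70% to 86% (range reading) and from 35% to 57% (strict). The levels are therefore not robust. The weak response to drift survives, and NAP hardly changes.
- The remark in Section 2.2 concerns interviews, screenings and assessment sessions. It is not evidence of linear drift over 24 weeks.

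None of this supplies a trend adjustment for NAP. Raw NAP absorbs drift whichever MLM is finally fitted.

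**Conclusion.** The point holds as a gap in how Section 8 handles drift, and it should be fixed. It is firmest for NAP, where the raw index is named and nothing offsets a trend: under assumed drift and no effect it shifts from 0.50 to about 0.55, 0.59 or 0.68. For the MLM the risk depends on a choice still open. At 0.5-SD drift the excess is modest; at 1-2 SD it is large. Pooling post ratings with coaching makes it larger, while a separate post step changes little.

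The sizes rest on assumed linear drift, SD, autocorrelation and a 5% test. The direction holds for any steady improvement. The documents do not support the stronger statement that drift will be credited to coaching, or that the design cannot separate the two.

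**What to change.** 1. Report a trend-adjusted NAP beside raw NAP for the baseline-versus-coaching comparison in Section 3. Take the slope from a model that lets it differ during coaching, because one common slope subtracts much of a gradual response. Do not read raw NAP as a coaching effect when a time trend is present.
2. Among the alternative models already promised, show the GAS effect with and without a time term that uses the staggered starts, and include a version with phase-by-time. Do not rely on time plus step alone.
3. State whether and how post-intervention ratings enter the MLM and NAP. Label pooled results and separate-post-step results as different analyses.

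Cost: SAP wording and a little code, with no new data. The SD of the trial-mean NAP is about 0.05 raw, 0.08 with a common slope and 0.10 with the phase-by-time slope. The MLM loses power as tabulated above, which is why the models should be shown together.

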4 STUDY POPULATION

We will enroll 50 participants aiming to have 25 eligible participants and 8-10 study completers.

Study completers are defined as Veterans who complete sufficient research tasks to conduct visual analysis for the multiple baseline design (i.e., at least 4 baseline data points that meet the stability criterion, initiate intervention within 2 weeks of scheduled intervention start date, and complete at least 4 intervention phase assessments) and complete the intervention (i.e., completed the Personal Health Inventory with the peer as the basis of Whole Health Coaching, defined a focus for coaching (Whole Health Coaching Stage II Phase II), set a goal (Whole Health Coaching Stage III Phase II), established an action step (Whole Health Coaching Stage III Phase II), and assessed the action taken (Whole Health Coaching Stage IV Phase I).

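### Section 8 offers pre-post effect sizes for later power calculations without an interval or a named analysis set; at about 8-10 Veterans the point estimate alone is too imprecise to size a trial

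*Combined protocol and SAP*

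**What the plan says.** Section 8 (Statistical Analyses) devotes most of its text to the primary outcome, GAS: multi-level modelling, visual inspection and a non-overlap effect size. The remaining outcomes get one sentence: "Other quantitative outcomes will be analyzed through descriptive statistics, and will be used to generate pre-post effect size estimates for Veteran outcomes", and the purpose given is "to establish initial estimates of efficacy for power estimates".

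The secondary outcomes are the PCL-5, IPF and CSQ. In Table 2 (Section 7.1) the PCL-5 and IPF are taken at the baseline, pre, post and follow-up assessments. The CSQ is taken at post only, so it cannot give a pre-post change.

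On numbers, Section 4 says "We will enroll 50 participants aiming to have 25 eligible participants and 8-10 study completers". It then says "Study completers are defined as Veterans who complete sufficient research tasks to conduct visual analysis for the multiple baseline design", and adds a list of intervention steps that must also be completed.

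The documents do not say which Veterans enter the pre-post effect sizes, what the change is divided by, or whether an interval will be reported. They also do not describe the later study that would use the figures.

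**The concern.** An effect size passed to a power calculation is normally entered as a single number, and required sample size varies with the inverse square of that number. A standardised change from very few people is uncertain enough that the implied sample size can move by an order of magnitude or more.

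This is sampling error. It would remain even if the change were measured against a perfect comparator, so it is separate from the lack of a control group. The consequence falls on the follow-on study. After a lucky result it would be too small; after an unlucky one it would be needlessly large or dropped. Because Section 8 plans no interval, a later planner would see no warning of this.

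**Working it through.** **No figure to reproduce.** The documents give counts (50, 25, 8-10) with no effect size, SD, alpha, power or precision target.

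**Inputs.**
- From Section 4: n = 8 and 10 (completer target) and n = 25 (eligible target, as the best case).
- Assumed: d is mean change divided by the SD of change, with observed values 0.5, 0.8 and 1.2. The later trial has two equal arms, two-sided alpha 0.05 and 80% power, and takes the same d.

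**Step 1: interval for d.** With t = d√n on n-1 degrees of freedom, the limits are the noncentrality values that put t at the 97.5th and 2.5th percentiles of the noncentral t, divided by √n. For d = 0.5 and n = 8, t = 0.5 × 2.828 = 1.414.

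**Step 2: implied size.** n per arm = 2(1.96 + 0.8416)²/d² = 15.70/d², rounded up. For d = 0.5, 15.70/0.25 = 62.8, so 63. The table uses unrounded limits.

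| Observed d (n per arm) | Veterans | 95% CI | n per arm at upper limit | n per arm at lower limit |
|---|---|---|---|---|
| 0.5 (63) | 8 | -0.25 to 1.22 | 11 | none finite |
| | 10 | -0.17 to 1.15 | 12 | none finite |
| | 25 | 0.08 to 0.91 | 19 | 2521 |
| 0.8 (25) | 8 | -0.03 to 1.59 | 7 | none finite |
| | 10 | 0.07 to 1.50 | 7 | 3713 |
| | 25 | 0.34 to 1.25 | 11 | 135 |
| 1.2 (11) | 8 | 0.25 to 2.10 | 4 | 251 |
| | 10 | 0.36 to 2.01 | 4 | 124 |
| | 25 | 0.68 to 1.71 | 6 | 35 |

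The interval excludes zero only when the observed d exceeds t(0.975, n-1)/√n, which is 0.84 at n=8, 0.72 at n=10 and 0.41 at n=25.

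**Step 3: real power of a trial sized on the point estimate.** Take a true d of 0.5. Real power is about Φ(0.5√(m/2) - 1.96) for m per arm.
- At m = 30, 0.5 × √15 = 1.936, which is under 1.96, so power is just under 50%. At m = 31, 0.5 × √15.5 = 1.969, so power is just over 50%.
- A trial gets 30 or fewer per arm when the observed d is at least √(15.70/30) = 0.723.
- The chance of that, given a positive observed d, comes from the noncentral t with noncentrality 0.5√n. At n=8 it is 0.312/0.921 = 34%; at n=10, 0.286/0.943 = 30%; at n=25, 0.169/0.994 = 17%. Simulation gives the same three figures.
- The observed d is zero or negative in 8% of studies at n=8 and 6% at n=10.

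**Step 4: why the definition matters.** If pre and post SDs are equal, d on the SD of change equals d on the raw SD divided by √(2(1-r)), where r is the pre-post correlation. A raw d of 0.5 becomes 0.5/√1.4 = 0.42 at r = 0.3 and 0.5/√0.4 = 0.79 at r = 0.8 (r assumed). Put into Step 2 using unrounded values, the same change implies 88 or 26 per arm.

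**The case against.** The strongest reply is that Section 8 promises little: descriptive statistics and estimates it calls initial. It sets no test or decision rule for these outcomes, describes no later trial, and does not say that the point estimate alone would size one. The two-arm design, alpha, power and carry-over of d are assumptions of this check. All of that stands, and it limits how far the point goes.

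A reader might infer several stronger things that the documents do not support:
- *That 8-10 is the sample for these effect sizes.* Section 4 sets that target for Veterans with enough data for visual analysis who also completed the intervention steps. A Veteran could supply both PCL-5 or IPF scores without qualifying, and 25 eligible are sought.
- *That the estimate is unusable, or that its purpose fails outright.* A wide initial estimate, read with its interval or a conservative limit, can still inform planning, especially if the effect is large. At n=25 and d=1.2 the implied range is 6 to 35 per arm.
- *That the interval always runs from harm to large benefit, with no finite size at its lower end.* This depends on the observed d. It is true at d=0.5 for n=8-10, but not at d=1.2.
- *That missing 80% power in more than half of cases shows a small-sample flaw.* That share is 56% at n=8, 55% at n=10, 51% at n=25 and 49% at n=100. It is close to a coin flip at any size, so only the below-50% figure is informative.

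What the reply does not remove is the stated use in power estimates combined with no interval, no analysis set and no definition. The word initial supplies none of these.

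**Conclusion.** The point holds in limited form. If the contributing set is near 8-10, the point estimate alone should not size a later trial: across observed d of 0.5 to 1.2, the sizes implied by the two confidence limits differ at least about 30-fold (124/4 = 31 at d=1.2, n=10). With a true d of 0.5, roughly one in three follow-on trials sized on a positive estimate would have real power below 50%. If all 25 eligible Veterans contributed, this falls to about one in six. These figures rest on the assumed n, effect definition and later design.

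The intervals cover sampling error only. Lack of a control, entry at a PCL-5 of 33 or more, and any restriction to completers would add bias that no interval shows.

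The GAS analysis and this trial's own conclusions are not affected. The correction is worth making because it is cheap, but it is not a fault in the main analysis.

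**What to change.** In Section 8:
1. State which Veterans enter the pre-post effect sizes, and which assessments are the pre and the post score.
2. State how the effect is standardised (SD of change or raw SD).
3. Report each PCL-5 and IPF effect with its 95% CI, labelled descriptive.
4. Say that the point estimate alone will not serve as the planning effect.
5. Base later sizing on a meaningful difference in PCL-5 or IPF points stated in advance, with a conservative confidence limit for the SD. The upper 95% limit is √((n-1)/χ²(0.025, n-1)) times the observed SD: 2.04 at n=8 and 1.83 at n=10.
6. Use the pre-post correlation only with a conservative limit, if at all. With an assumed observed r of 0.5, the Fisher interval is -0.32 to 0.89 at n=8 and -0.19 to 0.86 at n=10, so it is no more reliable than d.

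The cost is a few sentences and one interval calculation per outcome, with no new data. The downside is that the trial no longer claims to supply a stand-alone efficacy figure for power.

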9 SUPPORTING DOCUMENTATION AND OPERATIONAL CONSIDERATIONS

9.1 REGULATORY, ETHICAL, AND STUDY OVERSIGHT CONSIDERATIONS

9.1.1 INFORMED CONSENT PROCESS

At the one-time in-person baseline assessment, Veterans will be provided with comprehensive oral and written information about the study procedures, anticipated risks and benefits, and rights as a research participant (including the right to refuse participation or withdraw from the study at any time). Veterans

will be informed that participation (or lack of participation) in the research study will not affect their eligibility for care at the VA. Veterans will be asked to provide written informed consent and will be offered a copy of their signed informed consent document for their records. Limits of confidentiality and importance of Veterans' safety will be outlined.

